### **19.7. Interim Analysis and Criteria for Early Termination of the Study**

No explicit interim analyses are planned for this study.

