## **19. STATISTICAL PLAN**

This is a single-arm, open-label, Phase II study of abatacept + ixazomib + dexamethasone in relapsed, multiple myeloma patients.

Summary statistics for continuous variables will include the mean, standard deviation, percentiles and range (minimum/maximum). Categorical variables will be presented as frequencies and relative frequencies; and time-to-event variables will be summarized using Kaplan-Meier methods.

The analyses will be conducted using the intent-to-treat principle, where all patients who receive or attempt to receive treatment are included. All analyses will be conducted in SAS v9.4 (Cary, NC) at a significance level of 0.1.

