### **19.1. Sample Size Determination**

The sample size determination is based on the primary analysis of response rate. Prior studies have demonstrated a second-line treatment response rate of approximately 30% in this patient population (34), and we would consider a response rate for the proposed treatment combination (abatacept + ixazomib + dexamethasone) of 50-60% to be a clinically relevant improvement. Therefore, we will test the following hypotheses:

$$H_0: \pi = 0.3$$

$$H_A: \pi > 0.3$$

where  $\pi$  is the true response rate, using a one-sided Binomial exact test. If the true response rate for the proposed treatment combination is 60%, then our study design ( $n=19$ ) as a 90% chance of achieving statistical significance at  $\alpha = 0.1$ .

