#### 19.4. Primary Analyses

The primary objective is to determine the therapeutic efficacy (as measured by response rate) of abatacept + ixazomib + dexamethasone in multiple myeloma patients who have relapsed after treatment with their first proteasome inhibitor-containing regimen (excluding ixazomib) and have not been treated with a second proteasome inhibitor.

Previous studies have demonstrated a response rate of approximately 30% for ixazomib + dexamethasone as second line therapy in this patient population (34). We hypothesize that the proposed treatment combination (abatacept + ixazomib + dexamethasone) will improve the second-line response rate in this patient population. Therefore, we will test the following hypotheses:

$$H_0: \pi = 0.3$$

$$H_A: \pi > 0.3,$$

where  $\pi$  is the true response rate, using a one-sided Binomial exact test. A total of n=19 patients will be enrolled and if T=9 or more patients have a response, then the treatment combination will be considered promising; otherwise the treatment combination is not promising. Additionally, the response rate will be summarized using a 90% confidence interval obtained using Jeffrey's prior method.

**Replacement:** Patients that withdraw from the study prior to completing the first cycle of treatment due to toxicity, disease progression, or other treatment related reasons will be considered as 'non-responders' and included in the primary analysis.

Patients that withdraw from the study prior to completing the first cycle of treatment due to non-treatment related reasons will be considered 'unevaluable' for the primary outcome and will be replaced.

**Efficacy Analysis:** Responses to treatment will be measured by serum immunoglobulins, serum free kappa and lambda light chains, serum protein electrophoresis/immunofixation electrophoresis, and 24-hour urine protein electrophoresis/immunofixation. International uniform response criteria will be used. The anti-myeloma activity will be evaluated on an exploratory basis

Roswell Park Protocol No.: I 47217

and will be summarized using descriptive statistics or graphical methods. No formal comparison will be carried forth

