**20. PROVISIONS TO MONITOR THE DATA TO ENSURE THE SAFETY OF SUBJECTS**

The Roswell Park Data Safety Monitoring Committee will assess the progress of the study, the safety data, and critical efficacy endpoints (Phase I studies will be reviewed quarterly; Phase II, III and pilot investigator-initiated studies will be reviewed semi-annually). The DSMC will review the study and will make recommendations that include but not limited to; (a) continuation of the study, (b) modifications to the design, (c) suspension of or (d) termination of the study.

Roswell Park Protocol No.: I 47217

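### A cheap improvement: add a curtailment rule so that accrual stops once 11 final non-responders have put 9 of 19 out of reach

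*Combined protocol and SAP*

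**What the plan says.** Section 19.4 plans 19 patients, with the decision rule "if T=9 or more patients have a response, then the treatment combination will be considered promising; otherwise the treatment combination is not promising". Section 19.7, whose title covers criteria for early termination, contains one statement: "No explicit interim analyses are planned for this study".

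The numerical rules that can halt the study all concern toxicity: the six-patient lead-in (Sections 10.2 and 19.3) and the Bayesian chronic-toxicity rule (Section 19.8). Section 20 says that the monitoring committee "will assess the progress of the study, the safety data, and critical efficacy endpoints", semi-annually for Phase II studies, and may recommend suspension or termination. It gives no response-based criterion.

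Three other provisions matter here:
- Sections 4 and 7 describe 19 as a maximum, with accrual taking up to 4 years.
- Section 16 lets a response count at any time before new therapy starts and requires two consecutive assessments. No assessment time point is fixed for the primary endpoint.
- Section 19.4 counts treatment-related withdrawals in cycle 1 as non-responders and replaces withdrawals that are not treatment-related.

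**The concern.** The primary decision depends only on whether 9 responses are reached among 19 patients. When 11 patients have finally failed to respond, no later result can change it. Patients enrolled after that point receive an added immunosuppressive agent in a combination that Section 13 describes as untried, and they cannot affect the primary conclusion. With accrual spread over about four years, many outcomes could be known while enrolment is still open. The plan tells nobody to count them for this purpose.

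**Working it through.** **Inputs.** n = 19 and T = 9 (Section 19.4). The null rate is 0.30, from "Prior studies have demonstrated a second-line treatment response rate of approximately 30% in this patient population", and power is stated at a true rate of 0.60 (both Section 19.1). The test is run "using a one-sided Binomial exact test" (Section 19.1) and "at a significance level of 0.1" (Section 19). Accrual of 19 patients in 48 months (Sections 4 and 7) is one per 48/19 ≈ 2.5 months. The time until non-response is final is not given, so it is assumed below and varied.

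**1. The plan's own figure.**
- Type I error: P(X ≥ 9 | 19, 0.30) = 0.0839.
- Power: P(X ≥ 9 | 19, 0.60) = 0.9115, against the stated 90%. It reproduces.
- Neighbouring cut-offs confirm T = 9: T = 8 gives a type I error of 0.182, and T = 10 gives power of 0.814.

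**2. Point of no return.** 19 − 9 + 1 = 11 non-responders, which leaves at most 19 − 11 = 8 responses.

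**3. Error rates with curtailment.** Every trial stopped at the 11th final non-responder would have ended with 8 or fewer responses, so it was already in the not-promising set. P(declared promising) therefore remains P(X ≥ 9). Exact path enumeration returns 0.0839 at 0.30 and 0.9115 at 0.60, identical to step 1. This holds whatever the delay, provided that nobody counted as a final non-responder is later reclassified. At 0.50, the lower end of what Section 19.1 calls a rate "of 50-60% to be a clinically relevant improvement", power is 0.676 with or without the rule.

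**4. Upper bound on the saving (instant outcomes).** With p the true response rate and q = 1 − p, P(stop at patient t) = C(t − 1, 10) · q¹¹ · p^(t − 11) for t = 11 to 18; otherwise N = 19. At p = 0.30 the terms for t = 11 to 18 are 0.020, 0.065, 0.117, 0.153, 0.160, 0.144, 0.115 and 0.084. They sum to 0.859, and E[N] = 15.5. At 0.60, E[N] = 18.9 with a 0.058 chance of stopping early, only in trials already unable to reach 9.

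**5. With delay.** Simulation: exponential gaps between patients with mean 48/19 months. Non-response becomes final 2 months plus an exponential time after entry, with the total mean as shown. True rate 0.30:

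| Assumed mean delay (months) | E[N] | Patients spared (19 − E[N]) | Stops before 19 |
|---|---|---|---|
| 0 (bound, step 4) | 15.5 | 3.5 | 86% |
| 4 | 16.8 | 2.2 | 70% |
| 6 | 17.3 | 1.7 | 59% |
| 9 | 17.9 | 1.1 | 44% |
| 12 | 18.3 | 0.7 | 30% |
| 18 | 18.7 | 0.3 | 13% |

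A simpler model with a fixed lag, counted in patients enrolled meanwhile, agrees: lags of 1, 2, 3, 4 and 6 patients spare 2.6, 1.8, 1.2, 0.7 and 0.1. Savings are larger at lower true rates. At 0.10, E[N] is 13.8, 14.6, 15.7 and 16.6 for mean delays of 4, 6, 9 and 12 months.

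**6. Cost in estimation.** Sampling now depends on outcome. At 0.30 with instant outcomes, the mean of responses/N is 0.284 instead of 0.30, and coverage of the planned 90% Jeffreys interval is about 0.88 instead of 0.92. Both effects shrink with delay, because fewer trials are curtailed.

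**The case against.** The strongest reply is that a single-stage exact design is a legitimate, openly declared choice. It is complete and internally consistent, and nothing in the documents promises futility stopping. That stands: the absence of a rule is not an error.

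A reader might infer that the trial is bound to enrol 19 whatever happens. The documents do not support this. Sections 4 and 7 give 19 as a maximum, and Section 20 lets the committee recommend termination after looking at efficacy. What is missing is a numerical trigger.

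A reader might also take 15.5 patients and 86% as the expected benefit. Those figures need each outcome to be known before the next patient enters. Two consecutive assessments are required, and a patient with stable disease still on treatment can yet respond, so instant knowledge is not available. The rows with delay in the table are the relevant ones, and at long delays little is saved.

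Nor are later patients unprotected: the toxicity rules cover the new combination, and Section 2.1 describes the ixazomib and dexamethasone backbone as one standard-of-care regimen. This tempers the risk argument. It does not supply a reason to continue for a primary question already settled.

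Finally, curtailment is free only in error rate and power. It reduces the data for toxicity, progression-free and overall survival and the biomarker models, and it affects the response-rate estimate. That is a real cost, and a sponsor who wants all 19 patients for those purposes could reasonably say so.

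**Conclusion.** The point holds as a low-cost improvement. Under the planned default, accrual can continue after 9 of 19 has become unreachable, and no efficacy criterion prompts the committee to act. Stopping at the 11th final non-responder changes neither the type I error (0.084) nor the power (0.912 at 60%). At a true 30% it spares about 2.2 patients on average with a mean delay of 4 months, falling to 0.3 at 18 months. Those figures rest on the assumed delays and on steady accrual of 19 in 48 months; faster accrual would reduce them. The unchanged error rates do not rest on either assumption. They require only that the rule and the final analysis use the same definition of a non-responder.

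**What to change.** Add to Section 19.7, for the existing monitoring committee to apply:

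*Accrual stops when 11 patients included in the primary analysis are final non-responders (progression, death, new therapy or end of treatment without a confirmed response). The combination is then declared not promising. Patients already enrolled continue per protocol.*

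Use the same definition of a final non-responder in Section 19.4. Replaced, unevaluable patients do not count toward the 11. State in Section 19.4 that, if accrual is curtailed, the response rate and its 90% interval will be reported with a note that sampling was curtailed.

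The cost is a few lines of SAP text and a running count. Threshold, sample-size ceiling, type I error and power stay as they are. The price is less information for the secondary and exploratory analyses, plus the small bias and interval effect shown above, and it falls mostly on trials whose primary result is already negative. If the sponsor prefers to keep all 19 patients for those analyses, Section 19.7 should give that reason.

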### **19.8. Monitoring of Chronic Toxicities**

Upon completion of the DLT assessment period, patients will be monitored for chronic toxicities utilizing the same DLT/ AE criteria used during the DLT assessment period (see **Section 10.3**).

This monitoring will be done continuously using Bayesian methods. If the posterior probability is 0.80 or greater than 25% or more of treated subjects experience a chronic toxicity, the study will be suspended pending review. This posterior probability will be calculated from the study's accumulating data and a weakly informative prior distribution. If  $\pi$  denotes a random variable representing the proportion of subjects who will experience a chronic toxicity, we assume  $\pi$  has a beta distribution with parameters  $a = 1$  and  $b = 2$ .

Selected values of the posterior distribution  $PP(\pi \geq .25 | \text{chronic toxicities and prior})$  are shown in the table below. Also shown are the binomial probabilities of suspending the study for observed count of chronic toxicities. Note that the study-suspension rules using the Bayesian analysis do not correspond to traditional values of statistical significance, such as 0.05 or 0.10, because our purpose is not to demonstrate unexpected harm, but rather to ensure subject safety.

**Number of Subjects Observed to Have Treatment-Related Chronic Toxicities and Corresponding Posterior and Binomial Probabilities Needed to Suspend the Study**

Subjects	Treatment-Related Chronic Toxicities	$PP(\pi > 25\%)^*$	$Pr(X \geq r   p = .25)$
2	2	.949	.063
3	2	.896	.156
4	2	.831	.262
5	3	.929	.104
6	3	.886	.169
7	3	.834	.244
8	4	.921	.114
9	4	.885	.166
10	4	.842	.224
11	5	.920	.115
12	5	.888	.158
13	5	.852	.206
14	5	.810	.258
15	6	.893	.148
16	6	.861	.190
17	6	.825	.235
18	7	.898	.139
19	7	.870	.175

\* $\pi$  is the chronic toxicity rate. The minimum acceptable upper bound of treatment-related chronic toxicities is 25%.  $PP(\pi > 25\%)$  is the posterior probability that the chronic toxicity rate exceeds this 25% upper bound. This posterior probability of a chronic toxicity is calculated from the prior distribution, the number of subjects treated and the observed number of treatment-related chronic toxicities.

The table above presents the minimum number of subjects experiencing treatment-related chronic toxicities that would dictate suspension of the trial in accordance with the stopping rule. If a study is suspended for safety concerns, the research team will meet to discuss study termination or possible adjustments to the treatment combination.

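### Section 19.8 labels single-look binomial tails as probabilities of suspending the study; under the continuous rule a regimen at the 25% limit is suspended with probability 0.449, not 0.175

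*Combined protocol and SAP*

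**What the plan says.** Section 19.8 sets a Bayesian rule for suspending the study because of chronic toxicity. On timing it says: "This monitoring will be done continuously using Bayesian methods". The trigger is given as "If the posterior probability is 0.80 or greater than 25% or more of treated subjects experience a chronic toxicity", with "a weakly informative prior distribution" specified as Beta(1, 2). A table lists, for 2 to 19 subjects, a toxicity count r, the posterior probability that the rate exceeds 25%, and Pr(X ≥ r | p = .25). The text after the table says that the counts are the "minimum number of subjects experiencing treatment-related chronic toxicities that would dictate suspension of the trial in accordance with the stopping rule".

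The last column is described as follows: "Also shown are the binomial probabilities of suspending the study for observed count of chronic toxicities". The table title likewise ties the binomial probabilities to suspension of the study. The same section says that the rule is not meant to match conventional significance levels, because its purpose is subject safety. Neither Section 19.8 nor any other section gives a cumulative probability of suspension at any true rate.

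**The concern.** A tail probability at a fixed number of subjects equals the probability of suspension only when that number is the single point at which the rule is applied. Here the rule is applied throughout, so the chance of suspension builds up over looks and must be at least as large as the largest single-look tail. The column behaves differently: it runs .262 at 4 subjects, .104 at 5, .258 at 14 and .175 at 19. The probability of having been suspended cannot fall as subjects accrue.

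These are the only operating characteristics the plan offers for this rule, and Section 19.7 plans no explicit interim analysis. Someone who takes the descriptive sentence at its word would think that a regimen exactly at the 25% limit has roughly a 6% to 26% chance of suspension, depending on the row. Suspension leads to a meeting that may end the study or adjust the combination, and so interrupts the only test of the primary endpoint (9 or more responders among 19). The investigators and the monitoring committee should know how often to expect it.

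**Working it through.** **Inputs, all from the plan.** Suspend when P(π ≥ 0.25 | data) ≥ 0.80; prior Beta(1, 2); continuous monitoring, taken as one look after each subject, as tabulated (Section 19.8). Maximum 19 subjects: "A total of n=19 patients will be enrolled" (Section 19.4). Reference rate 0.25: "The minimum acceptable upper bound of treatment-related chronic toxicities is 25" per cent (footnote to the table). Cut-offs: r = 2 for n = 2–4; 3 for 5–7; 4 for 8–10; 5 for 11–14; 6 for 15–17; 7 for 18–19.

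**Step 1: reproduce the plan's figures.** After r toxicities in n subjects the posterior is Beta(1 + r, 2 + n − r). At n = 19, r = 7 this is Beta(8, 14), whose upper tail at 0.25 is 0.8701 (printed .870). With r = 6 it is 0.7436, below 0.80, so 7 is the minimum count. The binomial tail is

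Pr(X ≥ 7 | n = 19, p = 0.25) = 0.1749 (printed .175).

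All 18 posterior values and all 18 binomial values reproduce to within 0.001, and every r is the smallest count that meets the rule. The table is correct as a set of single-look quantities.

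**Step 2: the chance of suspension under the rule as stated.** Let f_n(k) be the probability of being unsuspended after n subjects with k toxicities. Then

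f_n(k) = f_{n−1}(k)(1 − p) + f_{n−1}(k − 1)p,

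and any mass at k ≥ r_n is removed and counted as suspended at n.

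At p = 0.25 the first looks can be done by hand:

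- The cut-off is 2 throughout n = 2–4, so suspension by n = 4 is 1 − 0.75⁴ − 4(0.25)(0.75³) = 1 − 0.3164 − 0.4219 = 0.2617.
- At n = 5 the cut-off rises to 3. An unsuspended trial has at most 1 toxicity at n = 4, so at most 2 at n = 5. The chance of suspension at this look is zero, yet the row shows .104.
- The probability of being unsuspended with 2 toxicities at n = 5 is 0.4219 × 0.25 = 0.1055. Suspension at n = 6 is therefore 0.1055 × 0.25 = 0.0264, and the cumulative figure is 0.2617 + 0.0264 = 0.2881.

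Continuing to n = 19:

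| Subjects | Cumulative probability of suspension (p = 0.25) | Column entry in that row |
|---|---|---|
| 4 | 0.262 | .262 |
| 7 | 0.333 | .244 |
| 10 | 0.372 | .224 |
| 14 | 0.422 | .258 |
| 19 | 0.449 (0.4485) | .175 |

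A simulation of 1,000,000 trials gives 0.449.

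**Step 3: other true rates.** The same recursion gives the expected number treated before suspension or completion as the sum, over subjects 1 to 19, of the probability that the trial is still running when that subject enters.

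| True rate | Cumulative suspension by n = 19 | Single look at n = 19 | Expected number treated |
|---|---|---|---|
| 10% | 0.067 | 0.002 | 18.0 |
| 15% | 0.160 | 0.016 | 16.8 |
| 20% | 0.291 | 0.068 | 15.2 |
| 25% | 0.449 | 0.175 | 13.3 |
| 30% | 0.608 | 0.334 | 11.3 |
| 40% | 0.855 | 0.692 | 7.7 |

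**Step 4: sensitivity to the look schedule, at a true 25% rate.**

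| Looks | Probability of suspension |
|---|---|
| After every subject, with the untabulated n = 1 look added | 0.517 |
| After every subject from n = 2 (as tabulated) | 0.449 |
| After every subject from n = 6 | 0.390 |
| At 6, 10, 14 and 19 | 0.355 |
| At 6, 12 and 19 | 0.288 |
| At 10 and 19 | 0.281 |
| At 6 and 19 | 0.263 |

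The n = 1 look is shown because one toxicity in one subject gives a posterior probability of 0.844, which meets the 0.80 rule although the table starts at 2.

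**The case against.** The best defence is that nothing in the table is miscalculated. The header defines the column exactly, and a careful reader can see from its falling values that each row stands alone. The posterior threshold governs action; the binomial column triggers nothing. The plan also warns against reading the rule in terms of conventional significance. Crossing leads to suspension pending review, not automatic termination, and frequent review at the limit of acceptability is arguably what the rule is for. Finally, 0.449 belongs to one schedule. Chronic monitoring starts only after the DLT period, six patients complete a cycle before the lead-in evaluation, and late events may arise out of enrolment order, so real looks may be fewer.

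Much of this stands. The fault is one of description, the boundary need not change, and the exact figure depends on the schedule. But the row-by-row reading does not rescue the sentence: at 5 subjects no unsuspended trial can cross, so .104 is not a probability of suspending at that look or by it. The significance disclaimer explains why the boundary is lenient about false alarms; it does not say that looks accumulate. Every schedule tried gives more than 0.175, and a look after each subject is what the plan states and tabulates.

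**Conclusion.** The concern holds: the description of the column is wrong as written. At a true chronic-toxicity rate of 25% the tabulated rule suspends the study with probability 0.449, about 2.6 times the last-row figure (0.449 / 0.175) and well above the largest entry of .262. At 15%, about one trial in six is suspended. The figures assume a look after each subject from 2 to 19, each subject's chronic-toxicity status known before the next look, and independent outcomes. With fewer or later looks the 25% figure lies between 0.263 and 0.390; with the look at 1 subject added it is 0.517. The direction of the error does not depend on these assumptions. No effect on the type I error of the primary test has been shown, and the rule errs on the side of safety.

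**What to change.** In Section 19.8, reword the sentence that introduces the last column, and the table title, to say that each entry is the tail probability at that single look, at a true rate of 25%. Add a short operating-characteristics table giving the cumulative probability of suspension and the expected number treated at true rates of 10, 15, 20, 25, 30 and 40%, and state the look schedule it assumes. If looks will be less frequent than one per subject, give the figures for the schedule intended. State also whether the rule applies at the first subject.

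The cost is a change of wording and one small table, and a stated figure becomes less favourable. The suspension rule, the sample size and the primary analysis stay as they are.
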